2 STUDY POPULATIONS

Definition of Study Populations

2.1.1 *Intent-to-Treat Population*

All randomized subjects will be included in the Intent-to-Treat (ITT) population. Subjects will be analysed according to randomized group.

2.1.2 *Full Analysis Set*

All randomized subjects with measurement of primary efficacy variable will be included in the Full Analysis Set (FAS). Subjects will be analysed according to randomized group.

2.1.3 *Per-Protocol Population*

All randomized subjects with no significant protocol violations will be included in the Per Protocol (PP) population. Subjects will be analysed according to actual embryo selection method. The Per Protocol population will be defined during the clean file meeting before the database lock without knowledge to which randomised group the patient belongs to.

2.1.4 *Safety Population*

All enrolled subjects who started one of the study embryo selections methods (i.e., in patients with a minimum of two early blastocysts) will be included in the safety population.

The final decisions regarding all the above study population will be taken at the Clean File meeting before the database lock.

STATISTISKA KONSULTGRUPPEN		Statistical Analysis Plan	
Protocol:		Protocol No: <protocol number>	
eValuating iDA Selection Ability. The VISA study.		Version: 2.0	Page 11 of 25

3 POOLABILITY OF INVESTIGATIVE SITES

The data from all investigative sites will be pooled based on the assumption of clinical comparability: the sites used a common protocol; the sponsor adequately monitored the study to assure protocol compliance; and the data gathering and validation mechanisms were the same across all study sites.

Analyses to justify pooling will include the following:

- The primary endpoint will be presented by site: Mean difference in percentages of clinical pregnancy with 95% CI.
- The justification for pooling all the data to estimate a common effect across study sites requires the homogeneity of response across study sites. An exact Pearson Chi-square test of the proportions of clinical pregnancies over sites will be generated to test whether the investigational sites differ with respect to primary study on the ITT population (only the site will be included in this analysis model). The test of homogeneity of response will be based on a two-sided significance test at the 0.10 level of significance.
- If the sites differ by this test then a second analysis will be done including study site and all baseline characteristics that have a $p < 0.10$ in the analysis of baseline variables by site to understand if the imbalance in the primary endpoint between sites is related to an imbalance in baseline characteristic.

The analysis of study sites may require the formation of pseudo-sites because the small study sites will not provide appropriate information to allow the analysis above. Study sites with fewer the 16 subjects will be

STATISTISKA KONSULTGRUPPEN		Statistical Analysis Plan	
Protocol:		Protocol No: <protocol number>	
eValuating iDA Selection Ability. The VISA study.		Version: 2.0	Page 12 of 25

combined into pseudo-sites for the poolability analysis using the following method. The smallest study site with less than 16 subjects will be combined with the next smallest study site. These two sites may be combined with a third site if the combined number of patients remain less than 16.

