### **10.3 Ovarian stimulation**

Ovarian stimulation will be performed with gonadotrophins (recombinant or urinary) as per routine protocol. The treating physician can decide on the starting dose of gonadotrophins and subsequent adjustments based on clinical judgment. Triggering of final oocyte maturation and oocyte retrieval will be performed as per protocol at each clinic.

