- The embryo for transfer will be selected by the embryologist based on the morphologic appearances on day 5, according to the Gardner criteria (Gardner et al., 2000) using the ranking guideline (Appendix 1, in CIP).
- Regardless of whether a transfer takes place any embryos that fulfil the criteria applied in the laboratory for cryopreservation will be cryopreserved (Appendix 1 in the clinical investigation protocol (CIP)). If there is doubt about whether an embryo is suitable for cryopreservation, embryos may be held over to day 6 and the decision will be made then.
- The order of rewarming and transfer of cryopreserved embryos for later transfer will be made according to Appendix 1 in the CIP based on the all the information that is available by day 6.

B. Treatment group: Embryo selection supported by iDAScore.

- The time-lapse videos will be analysed by iDA at 114-118 hours post insemination (hpi) and the embryo with the highest iDA score will be selected for fresh transfer on day 5.
- Any remaining viable embryos in this group will be cryopreserved if they have either:

STATISTISKA KONSULTGRUPPEN		Statistical Analysis Plan	
Protocol:		Protocol No: <protocol number>	
eValuating iDA Selection Ability. The VISA study.		Version: 2.0	Page 9 of 25

- reached Gardner Grade 3 or beyond AND would normally be cryopreserved or;
- have reached Gardner Grade 3 AND achieved a score on iDA of 5 or more.
- All other embryos will be cultured until day 6, re-scored at 138-142 hpi and according to the above criteria.
- The warming and transfer of embryos will be performed based on the ranking of the iDA score across the two days. The first embryo to be warmed will be the one with the highest iDAScore. If this embryo does not survive warming and is not suitable for transfer, the next embryo to be warmed will be selected based on the iDAScore, until an embryo is warmed and is suitable for transfer.

Embryo transfer will be performed using the clinic's routine methods. Luteal support will be administered using the standard protocol of each clinic. Both the treating clinician and the patient will remain blinded to the randomization outcome until after the first embryo transfer has been completed.

Sample Size calculation

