Main treatment variables will be summarized by treatment group for the FAS and PP populations and analysed according to the methods described in section “General Statistical Methodology” above.

Efficacy Analyses

Primary Efficacy Analysis

The primary statistical analyses will be calculation of the mean percentage difference with two-sided 95% confidence interval (CI) regarding the primary efficacy variable Clinical Pregnancy with fetal heartbeat after the first embryo transfer between the iDA group and the trained embryologist (standard) group unadjusted with Farrington-Manning 95% CI. If the lower limit of this 95% CI is larger than -5%, the non-inferiority margin, then non-inferiority is achieved. This analysis will be applied on the ITT population (primary) and PP population (sensitivity analysis). Any inconsistencies in these analyses will be discussed in the study report. Unadjusted relative risk (RR) with 95% CI will also be calculated. The Clinical pregnancy rate with exact 95% CI will be calculated for each of the randomised groups.

The following sensitivity analysis will also be performed adjusted for centre and stratification (minimization) variables:

To account for the lack of independence introduced by both the potential clustering within centers and the optimal randomization process (minimization), we will also estimate the difference in the clinical pregnancy probability between the two randomized groups with a 95% CI using a linear mixed effects regression model (with identity link function) with center as a random effect and fixed effects for the following variables used in the randomization:

- Woman’s age:

STATISTISKA KONSULTGRUPPEN		Statistical Analysis Plan	
Protocol:		Protocol No: <protocol number>	
eValuating iDA Selection Ability. The VISA study.		Version: 2.0	Page 18 of 25

< 25; 25 <= Age < 30; 30 <= Age < 35; 35 <= Age < 40; 5. 40 <= Age

- Number of previous stimulated IVF cycles leading to oocyte pick-up

1-5; 6 – 10; 11 – 15; 16 – 20; 21 – 25; 26 ->

- Number of oocytes:

• 2 – 5; 6 – 10; 11 – 15; 16 – 20; 21 - 25; 26 ->

- Fertilization method:

IVF for all; ICSI for all; ICSI for some

- Number of 2PN oocytes

• 2 – 5; 6 – 10; 11 – 15; 16 – 20; 21 - 25; 26 ->

- Center.

Adjustment with centre as random effect, fertilization method as class variable and the other four as continuous variables.

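### The only formal poolability test in the SAP has no treatment term, so it cannot show whether the iDA-minus-embryologist difference is the same across sites (minor)

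*SAP*

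**What the plan says.** SAP section 3 pools at the outset on a stated premise: "The data from all investigative sites will be pooled based on the assumption of clinical comparability". It then lists analyses to justify this.

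- The first is descriptive: "The primary endpoint will be presented by site: Mean difference in percentages of clinical pregnancy with 95% CI". The groups are not named there. SAP section 5, which also plans the primary analysis for each centre, and Table 14.2.1.5 make clear that this is the difference between the randomized groups. Protocol 14.7 plans the same.
- The second gives the purpose, "The justification for pooling all the data to estimate a common effect across study sites requires the homogeneity of response across study sites", and then the test: "An exact Pearson Chi-square test of the proportions of clinical pregnancies over sites will be generated". It is run on the ITT population at the two-sided 0.10 level, and "only the site will be included in this analysis model".
- If sites differ, a second model adds baseline characteristics to site. Treatment is not named in it.

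Sites with fewer than 16 subjects are merged into pseudo-sites. The results go to Table 14.2.1.6.

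No other section tests whether the treatment difference varies by site. SAP 5.1.4 lists maternal age, number of blastocysts and freeze-all as interaction variables, and not site. The adjusted sensitivity model in SAP section 5 has centre as a random effect but no treatment-by-centre term.

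**The concern.** A common effect is a statement about the iDA-minus-embryologist difference. The planned test collapses the arms and asks whether clinics have different pregnancy rates. If response is read as the pregnancy rate, the test fits that word, but it still does not address the common effect named in the same sentence.

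The documents give reasons to expect clinic base rates to differ in both arms alike. Protocol 10.3: "Triggering of final oocyte maturation and oocyte retrieval will be performed as per protocol at each clinic". SAP section 1: "Luteal support will be administered using the standard protocol of each clinic". The adjusted analysis in SAP section 5 is itself introduced "To account for the lack of independence introduced by both the potential clustering within centers". Such differences leave the treatment effect untouched but can make the site test positive.

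At stake is what Table 14.2.1.6 can support. It could raise a false alarm about pooling, or offer reassurance about a common effect that was never examined.

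**Working it through.** **Inputs from the documents.** Control rate 35.4%, 5 points more in the iDA group, margin -5 points, 90% power, 1:1 allocation, 520 per group (SAP section 1, sample size); 15 centres (SAP section 1; 14-15 in the footnote to SAP 4.1.1); test level 0.10 (SAP section 3).

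**Assumed, because the documents give neither.** Site sizes (15 equal sites of 68, 34 per arm; 15 x 68 = 1,020, close to the planned 1,040) and the between-site spread. Site deviations are taken as normal.

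**1. The plan's own figure.** (1.960 + 1.282)² x (0.354 x 0.646 + 0.404 x 0.596) / (0.05 + 0.05)² = 10.51 x 0.4695 / 0.01 = 493.3, so 494 per group; 494 / 0.95 = 520. This reproduces the plan and confirms the working rates of 35.4% and 40.4%.

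**2. What the site-only test measures.** X² = Σ nₛ(pₛ - p̄)² / [p̄(1 - p̄)] on 14 df, critical value 21.06, where pₛ is the two-arm rate at site s. The sampling variance of pₛ is 0.379 x 0.621 / 68 = 0.00346 (SD 5.88 points). If true site rates have SD σ, X² behaves roughly like (1 + σ²/0.00346) times a chi-square on 14 df. With σ = 5 points and the same effect everywhere:

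- factor = 1 + 0.0025/0.00346 = 1.72
- P(χ²₁₄ > 21.06/1.72 = 12.23) = 59%; simulation gives 58.2%.

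**3. What a risk-difference homogeneity test measures.** Q = Σ wₛ(Dₛ - D̄)², with Dₛ the treatment difference at site s and wₛ the inverse of its variance. SE(Dₛ) = √(0.354 x 0.646/34 + 0.404 x 0.596/34) = 11.75 points, so one site's 95% CI is about ±1.96 x 11.75 = ±23.0 points. A rate shift shared by both arms cancels from Dₛ. With an effect SD of 10 points the factor is 1 + 0.0100/0.01381 = 1.72, again about 59%.

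**4. Why the site test cannot attribute.** If only the control arm varies, with SD 10 points, the two-arm rate varies with SD 10/2 = 5 points. To the site test this is the situation in step 2.

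**5. Simulation.** 20,000 trials per scenario, asymptotic chi-square in place of the exact test, minimization not modelled. Percentage rejecting at 0.10:

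| Scenario | Spread (SD, points) | Site-only test | Risk-difference test |
|---|---|---|---|
| No variation | 0 | 10.0 | 10.1 |
| Common effect, site rates vary | 1 / 2 / 3 / 4 | 11.5 / 16.8 / 26.8 / 41.6 | 9.9-10.4 throughout |
| Common effect, site rates vary | 5 / 6 / 8 | 58.2 / 74.3 / 92.2 | 9.9-10.4 throughout |
| Effect varies, overall site rates equal | 3 / 5 / 10 / 15 | 9.7 / 9.6 / 9.4 / 8.4 | 13.9 / 21.3 / 59.6 / 90.0 |
| Only the control arm varies | 3 / 5 / 10 / 15 | 13.8 / 20.9 / 58.0 / 88.7 | 13.6 / 22.4 / 60.0 / 89.9 |
| Only the iDA arm varies | 3 / 5 / 10 / 15 | 13.4 / 20.6 / 57.8 / 89.0 | 14.2 / 22.2 / 60.6 / 90.3 |

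**6. Other layouts.** With a common effect and site-rate SD 4 points, the site-only test rejects in 42.7% (14 sites of 74) and 41.0% (unequal sites of 16 to 180, total 1,044). The risk-difference test stays between 9.7% and 10.8% in these layouts.

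**7. What non-rejection leaves open.** The Q-profile upper limit for the between-site SD is 11.75 x √(Q/5.629 - 1). At Q = 14, the largest value that gives a truncated moment estimate of 0, it is 14.3 points; at Q = 10 it is 10.4; at Q = 7 it is 5.8.

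**The case against.** The strongest reply is that the by-site differences belong to the same list of poolability analyses. A reader facing a positive site test can look at each clinic's treatment difference with its CI, and centre is a minimization factor. This stands in part. One might infer from the site-only test that the plan has no treatment-by-site information at all; the documents say otherwise in SAP sections 3 and 5, Table 14.2.1.5 and Protocol 14.7. What is missing is a test or summary of whether the differences agree, and fifteen intervals of about ±23 points do not supply that by eye.

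Second, one might infer that the test is blind to a varying effect. It is not. It misses variation when the arms move in opposite directions and leave the overall site rate unchanged, and nothing in the documents suggests such a mechanism. The mechanism the documents do suggest is that embryo ranking may differ between laboratories (Protocol 7.2, which limits this by asking them to follow Appendix 1). That acts on the control arm, and both tests detect it about equally. So the gain from the change is attribution more than power. The matching 58% figures rest on assumed spreads of 5 and 10 points, but step 4 shows why a match of this kind must arise.

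Third, the proposed test is weak against modest heterogeneity: about 14% power at an effect SD of 3 points and 22% at 5, against 10% by chance. This stands, and is why the test should be reported with an interval for the between-site SD.

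**Conclusion.** The point holds and is minor. The one formal test offered as justification for a common effect does not examine the treatment difference. A positive result cannot be attributed to a varying effect: about 58% rejection arises both from a fully common effect with a site-rate SD of 5 points and from a control-arm effect SD of 10 points. A negative result does not establish a common effect.

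A reader might go further and infer that pooling or the non-inferiority conclusion is in doubt. The documents do not support that. Pooling rests on assumed comparability whatever the test shows, a positive test leads only to an explanatory model, and the primary estimate, its CI and the decision rule do not depend on it. The harm is confined to Table 14.2.1.6 and the text built on it.

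The absence of a treatment term is read directly from the SAP. The rejection rates depend on the assumed spreads, site sizes and normal site deviations, and on the simulation's simplifications (asymptotic test, no minimization).

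**What to change.** In SAP section 3:

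- Make the homogeneity analysis a treatment-by-site test of the risk difference on the primary endpoint: ITT, 0.10 level, same pseudo-site rule. Use Cochran's Q, with each site's difference weighted by the inverse of a variance built from the pooled within-site variance of each arm, referred to chi-square on sites minus 1 df.
- Report it in Table 14.2.1.6 with the between-site SD of the difference (truncated moment estimate) and its Q-profile 95% CI, beside the by-site differences already planned.
- Keep the site-only chi-square, labelled as a description of base rates only.
- State that rejection leads to presentation and discussion of these results and does not change the primary analysis.
- State that non-rejection does not prove a common effect, giving the power figures above and their basis (15 equal sites of 68). If an upper limit is quoted for a zero estimate, word it as up to about 14 points, depending on Q; it is not about 14 points in every such case.

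Cost: one SAP paragraph and a few lines of code for an existing table. No new data are needed and the primary analysis is unchanged.

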4 STUDY VARIABLES

Baseline Variables

4.1.1 Demographics and Baseline Characteristics

1. Age (maternal*/paternal), continuous variables.
2. Reason for infertility (couple), categorical variable.
3. Height and weight (mat.), continuous variables
4. BMI (mat.), continuous variable
5. Type of menstruation (mat.), dichotomous variable
6. Number of previous stimulated IVF cycles leading to oocyte pick-up (couple)*, ordered categorical variable (7 categories)
7. Previous pregnancies in current relationship, ordered categorical variable (5 categories)

Treatment variables

1. FSH starting dosage, continuous variable
2. FSH total dosage, continuous variable
3. GnRH downregulation (agonist/ antagonist)
4. Source of sperm, categorical variable (6 categories)
5. Duration of ovarian stimulation, continuous variable.
6. Number of oocytes*, both as continuous variable and ordered categorical variable (7 categories)

STATISTISKA KONSULTGRUPPEN		Statistical Analysis Plan	
Protocol:		Protocol No: <protocol number>	
eValuating iDA Selection Ability. The VISA study.		Version: 2.0	Page 13 of 25

7. Method of fertilization (ICSI/Standard IVF/Combined)* Categorical variable
8. Number of normally fertilized oocytes (2PN)*, continuous variable
9. Number of blastocysts at Gardner Scale 2 or beyond by day 5 (Early blastocysts), continuous variable
10. Proportion of cycles where the embryo selected by the embryologist had the highest iDAScore (Only in the iDAScore group).
11. Number of cryopreserved embryos on day 5 and 6, continuous variable
12. Morphological score of the transferred embryo, continuous variable
13. iDAScore® (treatment group) of the transferred embryo, continuous variable
14. Type (categorical variable) and duration (continuous variable) of luteal phase support

*) These variables are used in a deterministic minimization procedure together with center during randomization. All variables are entered as Categorical variables: Age (5 cat.), number of earlier IVF cycles (7 cat.), number of oocytes (7 categories), fertilization method (3 cat.), number of 2PN oocytes (7 categories) and center (14-15 centers).

Efficacy Variables

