### **10.4 Embryology and randomization-blinding-allocation concealment**

Once the oocytes have been retrieved, all embryos will be fertilized by the method of IVF or ICSI as per the individual clinical decision-making and will be incubated in the Embryoscope system until day 5 or 6. As per normal embryoscope protocol, IVF-fertilized embryos will normally be placed in the embryoscope on day 1 and ICSI-fertilized embryos will be placed in the embryoscope on day 0. Exceptions to this can be made due to logistical reasons.

[figure not shown]
All embryos will be incubated using the Embryoscope time-lapse system. Embryo glue will be used as a transfer media in every case.

No analysis of the embryo will be performed by iDAScore until randomization has occurred and no other time lapse algorithms will be applied to the embryos of patients who have been recruited to this study. After randomization, iDAScore will only be applied to the treatment group.

On day 5 an embryologist will score all embryos according to the Gardner scale by visual selection using the Embryoscope software and make a preliminary decision on which embryo is prioritized for embryo transfer. If two or more early blastocysts are available (i.e. at the developmental stage of 2 or more according to the Gardner scale) between 114 and 118 hours post insemination (hpi), the patient is randomized using a 1:1 ratio. If there are fewer than two early blastocysts, randomization will not take place, and this will be recorded in the eCRF.

If randomized to the control group, the preliminary decision on embryo prioritization for transfer remains unchanged. If, however, the patient is randomized into the treatment group, the sequences of all normally fertilized embryos will be analyzed using the iDAScore software and the embryo with the highest score is prioritized for transfer.

Randomization will be performed with the use of a randomization module within the eCFR program. If, for some reason, randomization from within the eCRF is not possible, manual randomization will be performed by flipping a coin and the randomization outcome shall be registered once the database is accessible.

*Patients will be randomly allocated to two different study groups:*

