### 14.2 Descriptive statistics of baseline data

| Main demographic parameters (Demographics and baseline characteristics)   | Main treatment parameters (Treatment variables)  |
|---|--|
| 
 
1. Age (maternal*/paternal)
 
2. Reason for infertility (couple)
 
3. Height and weight (mat.)
 
4. BMI (mat.)
 
5. Type of menstruation (mat.)
 
6. Number of previous stimulated IVF cycles leading to oocyte pick-up (couple)*
 
7. Previous pregnancies in current relationship
 
8. Previous appearance of a FH at week 6-9, in current relationship
 
9. Previous births, after week 20 of gestation, in current relationship
 
 | 
 
1. FSH brand and starting dosage
 
2. FSH total dosage
 
3. GnRH downregulation (agonist/antagonist)
 
4. Source of sperm
 
5. Duration of ovarian stimulation
 
6. Number of oocytes*
 
7. Method of fertilization (ICSI/Standard IVF/Combined)*
 
8. Number of normally fertilized oocytes (2PN)*
 
9. Number of embryos available for selection
 
10. Number of cryopreserved embryos on day 5 and 6
 
11. Morphological score of the transferred embryo
 
12. iDAScore® (treatment group) of the transferred embryo
 
13. Did AI change the decision of the embryologist? (Y/N)
 
14. Type and duration of LH support
 
 |
| 
*) These parameters are used for stratification during randomisation
   |  |

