1 STUDY DETAILS

Study Objectives

The **primary objective** for this study is to investigate whether selection of a single blastocyst for transfer using the deep learning-based support tool called iDAScore results in a non-inferior clinical pregnancy rate compared to when the selection is performed by trained embryologists using conventional morphology only. Clinical pregnancy is defined in this study as the detection of a fetal heartbeat (FHB) by ultrasound after 42 days of gestation (week 6) (including ectopic pregnancies, as per the ICMART definition).

The **secondary objectives** for this study are:

To investigate whether blastocyst selection supported by iDAScore results in non-inferior rates of the below parameters compared to when embryo selection performed by trained embryologists using conventional morphology only:

1. Live birth rate* (defined as the number of patients with at least one live birth after 22 completed weeks of gestation. If the exact gestational age is not known then a birth weight of ≥ 500 gr can be used as a cut-off).
2. Positive β -hCG rate (defined as the number of patients with a positive β -hCG, determined by a hCG measurement from a blood sample or using urinary sticks).
3. Rate of non-viable pregnancies (defined as the difference between number of clinical pregnancies (excluding ectopic pregnancies) and number of positive β -hCG pregnancies)
4. Ongoing pregnancy rate* (defined as the number of patients with a viable pregnancy at ≥ 12 weeks of gestation)

*These secondary parameters will not be included in the first statistical analysis and report as these will not be available until approximately 12 months after the initial data collection.

STATISTISKA KONSULTGRUPPEN		Statistical Analysis Plan	
Protocol:		Protocol No: <protocol number>	
eValuating iDA Selection Ability. The VISA study.		Version: 2.0	Page 8 of 25

Study Design

This is a non-inferiority, prospective parallel group, double blind, randomized controlled trial in 15 IVF centres in 4 countries (Australia, Denmark, Sweden and United Kingdom).

Treatment Groups

Patients will be randomly allocated (1:1) to two different study groups if at least two embryos have developed to the blastocysts stage (Gardner score 2 or higher):

A. Control group: Embryo selection by standard morphologic criteria.

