It is estimated from the results in clinics that clinical pregnancy is estimated to be 35.4% for trained embryologists. If non-inferiority margin is defined as - 5%, the lower limit of the two-sided 95% confidence interval (CI) for the difference between iDAScore group and Trained embryologist group shall not be less than -5% with a probability of 90% ($\beta=10\%$), with an estimation of 5% or more clinical pregnancies in iDAScore group, 494 women per randomization group is needed to show non- inferiority with two-sided Farrington-Manning test. For protection against a 5% loss to follow-up, 1040 patients in total, 520 per group, are needed for recruitment.

STATISTISKA KONSULTGRUPPEN		Statistical Analysis Plan	
Protocol:		Protocol No: <protocol number>	
eValuating iDA Selection Ability. The VISA study.		Version: 2.0	Page 10 of 25

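### Deterministic minimisation with centre as a factor lets laboratory staff guess the next arm from their own centre's tally about 63% of the time, just before they judge eligibility; a random element would reduce this cheaply

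*SAP*

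**What the plan says.** The SAP footnote to the treatment variables (4.1.1) states: "These variables are used in a deterministic minimization procedure together with center during randomization". It lists age (5 levels), previous cycles (7), oocytes (7), fertilisation method (3), 2PN oocytes (7) and centre (14-15). The primary efficacy analysis section of the SAP mentions minimisation again. Neither place gives an assignment probability, factor weights, an imbalance measure or a tie rule.

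The protocol describes the method differently. Section 14.2 marks five variables, not centre, and says "These parameters are used for stratification during randomisation"; section 9.3 also speaks of stratification. Section 10.4 says only that "the patient is randomized using a 1:1 ratio" through an eCRF module, with a coin flip if the module is unavailable.

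On blinding, SAP section 1 calls the trial a "double blind, randomized controlled trial in 15 IVF centres in 4 countries". Protocol 9.3 and 10.4 name only the treating clinician and the patient as blinded. Under 10.4 the embryologist grades all embryos on day 5 and makes a preliminary choice; the patient is randomised if at least two embryos are at stage 2 or beyond; iDAScore is then applied in the treatment arm only.

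**The concern.** Minimisation without a random element usually sends the next patient to the arm that is behind. With centre as a factor, the arm behind at a given centre tends to be the one chosen, and the laboratory can follow that tally without data from elsewhere.

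The guess would be available when two judgements are made. One is whether a second embryo counts as stage 2, which decides entry. The other is the preliminary choice, which becomes the control-arm choice unchanged. If either were influenced by the expected arm, the groups would differ in prognosis or in the care given to the control selection. The primary analysis is unadjusted. The planned adjusted analysis uses centre and the minimisation variables, but neither early-blastocyst count nor grade.

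**Working it through.** **Plan's own figure.** The documents give no figure for predictability; the simulation takes only the trial size from them. That size reproduces. With rates 0.354 and 0.404, margin 0.05, one-sided 0.025 and 90% power:

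n = (1.960 + 1.282)² × (0.354×0.646 + 0.404×0.596) / (0.05 + 0.05)² = 10.51 × 0.4695 / 0.01 ≈ 493.3, so 494 per group.

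494 / 0.95 = 520 per group, which matches "1040 patients in total, 520 per group, are needed for recruitment". That is 1040/15 ≈ 69 to 1040/14 ≈ 74 patients per centre.

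**Simulation.**
- From the documents: 1,040 patients, 1:1 allocation, six factors with the levels in SAP 4.1.1, and 14 or 15 centres. The SAP's analysis section lists six rather than seven bands for three factors; this does not affect the conclusion.
- Assumed: category frequencies (uniform and skewed), centre sizes (equal and skewed), factor weights, imbalance measure and tie rule (random or fixed).
- Guess: the arm with fewer patients at the same centre; 50:50 if level.

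**Equal weights, deterministic, range or sum-of-differences measure.** The tally is uneven for about 72% of patients, and the guess is then right about 68-69% of the time. Overall: 0.72 × 0.68 + 0.28 × 0.50 = 0.63. Results run from 63% to 64% across the assumed frequencies, centre sizes and tie rules.

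**Other settings, deterministic:**

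| Measure | Centre weight | Correct guesses |
|---|---|---|
| Range | 0.5 | 58% |
| Sum of differences | 0.5 / 1 / 2 / 6 | 60% / 63% / 67% / 73% |
| Proportional | 0.5 / 1 / 2 | 65% / 69% / 72% |
| Sum or proportional | 0 (centre not a factor) | about 50% |

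The ceiling for this guess is 75%: if centre decided everything, the tally would alternate between level (50% right) and one apart (100% right).

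**With a random element, equal weights.** At 0.8 the guess is right about 58-59% of the time (62% with the proportional measure). At 0.7 it is about 55-56% with the range or sum measure. Taking 63.5% and 58.5%, 0.8 removes (63.5 − 58.5)/(63.5 − 50) = 37% of the excess over chance. Mean within-centre imbalance rises from about 1.4 to about 2.1-2.4 patients at 0.8.

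**What a guess could do.** Let f be the share of candidates who are borderline at the gate, d their deficit in pregnancy rate (points) and g the guess accuracy. Suppose every borderline patient is turned away whenever iDAScore is the predicted arm. The borderline share is then f(1−g)/[f(1−g)+1−f] in the iDAScore arm and fg/[fg+1−f] in the control arm. The false advantage for iDAScore is d times the difference. The values of f and d are assumptions.
- f = 0.05, d = 10, g = 0.63: shares 1.91% and 3.21%; bias 0.13 points.
- f = 0.10, d = 20, g = 0.63: shares 3.95% and 6.54%; bias 0.52 points.
- f = 0.30, d = 20, g = 0.63: shares 13.69% and 21.26%; bias 1.5 points.
- With g = 0.58 (probability 0.8), the first and last become 0.08 and 0.93 points.

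Even stacking the last case on the highest simulated accuracy (g = 0.73: shares 10.37% and 23.83%) gives 2.7 points, still below the margin of 5. Steering in the other direction would reverse the sign.

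**The case against.** The strongest reply is that the opening is narrow and guarded. Consent precedes oocyte pick-up (protocol 10.2), so the expected arm on day 5 cannot steer consent. The preliminary choice is made before randomisation expressly to reduce bias (9.3). Stage 2 has a written definition (Appendix 1) and a fixed window of 114-118 hours. Failures at the gate are recorded in the eCRF, and the SAP plans a flow chart covering eligibility. In the treatment arm the highest iDAScore takes priority. These points stand, and they are why the bias figures are small. They do not remove the predictability at the gate: stage 1 and stage 2 are separated by a visual call on whether the blastocoel fills half the embryo, and protocol sections 6 and 7.2 acknowledge observer variability.

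It is also fair to say that no text states that laboratory staff know every past allocation. Access is inferred from the workflow; who operates the module, how staff rotate and whether anyone keeps a tally are not described. Ties (about 11-17% of allocations with the range or sum measure) and the coin-flip back-up add some chance, but too little to change the result.

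A reader might infer that site staff can know the next arm exactly. That would need factor totals from all centres, which they are not said to have; with them, a guess would be right 91-95% of the time. A reader might also infer selection bias that no analysis could remove. The documents show no steering, motive or direction, and oocyte and 2PN counts in the adjusted analysis may capture part of any imbalance.

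**Conclusion.** The concern holds as a modest weakness in allocation concealment, worth correcting because the remedy is cheap. The deterministic rule and the role of centre are the SAP's own statements; that the laboratory can see each arm follows from the workflow. Correct guesses of about 63-64% rest on assumed equal weights and a range or sum measure, and the spread of about 58-73% reflects what the SAP leaves unspecified. The 0.1 to 1.5 points of possible bias are illustrative, use the equal-weight accuracy and require deliberate, consistent gaming. They do not show that the result is biased or that non-inferiority would be wrongly declared. Separately, the protocol and SAP describe the allocation method differently and should be reconciled.

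**What to change.** - **Allocations still to be made:** assign the imbalance-minimising arm with probability about 0.8, or lower (such as 0.7) if more protection is wanted. The cost is a changed setting in the randomisation module, with its validation and documentation, and the small loss of centre balance shown above, larger again at 0.7. This reduces predictability without abolishing it. Protocol 9.11 planned enrolment from March 2020 to September 2022, so it may reach few patients or none.
- **Documents:** in protocol 9.3 and 14.2 and in SAP 4.1.1, describe minimisation with a random element and centre as a factor. Give the probability, weights, imbalance measure and tie rule. State whether laboratory staff can see allocations, and align the SAP's double-blind label with that.
- **Patients already allocated:** report that allocation was deterministic. Compare early-blastocyst count between arms in all randomised patients; the SAP already lists this variable for summary by group, so it need only be named as a check. Compare the rate of gate exclusions according to which arm was behind at that centre at the time, using the eCRF exclusion records and the time-ordered allocation log. Both are descriptive and need no new data if those records are dated.
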